#### 9.2.9.1 Pharmacokinetic Blood Sampling

The plasma concentration/time curves of CBD and its major metabolites will be assessed at Visits 3 and 10 for patients weighing more than 20 kg. Where appropriate, blood samples will be taken as follows:

- One sample pre-dose (i.e., prior to administration of IMP).
- One sample between 2 and 3 hours post-dose.
- One sample between 4 and 6 hours post-dose.
- One sample between 8 and 10 hours post-dose (patients 18 years and above only).

There must be a minimum period of at least two hours between each of the blood sampling time points. In the event of an AE that, in the opinion of the investigator, is related to a concomitant AED, additional blood samples may be collected.

For patients who undergo PK blood sampling, the patient/caregiver will record all meal times and the types of meals consumed by the patient during all PK testing days (Visits 3 and 10).

Analysis of all pharmacokinetic samples will be conducted at a central clinical laboratory. Sample volume requirements and processing procedures will also be detailed in a separate laboratory manual. The patient/caregiver must be advised that it may not be safe for them to undertake further blood tests within one month of any study-related blood draws and to inform the investigator if they suffered any blood loss during the one-month period leading up to a planned blood draw.

#### 9.2.9.2 Determination of Plasma Concentrations of Concomitant Antiepileptic Drugs

Plasma concentrations of concomitant AEDs will be assessed at Visits 3, 5, 7, 9 and 10/ the Withdrawal visit (if possible) during the blinded phase and at Visits B2, B3, B4 and all subsequent Assessment Visits during the OLE. Samples will be collected for all patients provided that the risk/benefit outcome is favorable in the investigator's opinion. At each visit, blood samples will be taken prior to administration of IMP. Patients will be instructed to record the dosing time of their concomitant AEDs in the diary.

Additional blood samples may be taken for AED monitoring if there is a suspicion of changes in AED levels, with the aim to keep the AED plasma levels within the patient's therapeutic level. AED doses should be adjusted, as appropriate, following discussion with the GW medical monitor in order to maintain stable AED plasma concentrations.

### 9.2.9.3 Determination of Mutation Status of the *TSC1* and *TSC2* Genes

If the mutation status of *TSC1* and *TSC2* is unknown at screening, genetic analysis will be carried out if the patient/parent(s)/legal representative provides consent (a blood sample will be taken during Visit 1).

#### 9.2.10 Interactive Voice Response System

The IVRS will be used to collect patient reported diary data (refer to Section 9.2.11), to assign patients to treatment groups and to provide treatment allocation information in the event of patient unblinding. The IVRS will also be used to manage IMP supply.

A member of the study team must contact the IVRS at each clinic visit in order to:

- Allocate a patient number at screening (Visit 1).
- Randomize a patient (Visit 3).
- Obtain dispensing information (Visits 3, 4, 5, 6, 7, 9 and during OLE).

• Provide completion/taper/premature termination information (Visit 10).

Training will be given to all centers prior to the start of the study.

#### 9.2.11 Patient Diary

A diary will be completed daily throughout the study. Patients or their caregivers will be instructed on how to complete the diary and will be asked to record information daily. The number and type of seizures and the severity of focal seizures as well as information on AEs, concomitant AEDs and rescue medication will be collected each day from baseline (Visit 2). Information on IMP intake will also be recorded each day from randomization (Visit 3) until completion of dosing or withdrawal (Visit 10/Withdrawal visit).

Seizure information, including the number and seizure subtype, as well as the severity of focal seizures and the number of episodes of *status epilepticus* will be collected through an IVRS telephone diary completed daily throughout the blinded phase of the study by the patient or their caregiver. This IVRS telephone diary will be completed on a weekly basis during the OLE. The patient or their caregiver will also complete a paper diary daily to record AEs, concomitant AEDs, IMP intake and rescue medication throughout the study.

The following seizure subtypes will be collected daily in the IVRS telephone diary:

- Focal motor seizures without impairment of consciousness or awareness#
- Focal seizures with impairment of consciousness or awareness#
- Focal seizures evolving to bilateral generalized convulsive seizures#
- Generalized seizures:
  - Tonic–clonic#
  - Tonic#
  - Clonic#
  - Atonic#
- 'Other' seizures:
  - Absence seizures\*\*
  - Myoclonic seizures\*\*

- Focal sensory seizures\*\*
- Infantile/epileptic spasms\*\*
- Episodes of status epilepticus

# To be included in primary seizure endpoint.

\*\* To be included in composite 'other' seizure count.

For the purposes of calculating the composite seizure score, the severity of focal seizures will be assessed according to the following criteria:

- Type 1 Focal motor seizures without impairment of consciousness or awareness.
- Type 2 Focal seizures with impairment of consciousness or awareness.
- Type 3 Focal seizures evolving to bilateral convulsive seizures.

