#### SPONSOR: GW RESEARCH LIMITED

patients less than 18 years of age). Provided that the risk/benefit outcome is favorable in the investigator's opinion, prior to the first daily dose of IMP, a blood sample will be taken for analysis of plasma concentrations of concomitant AEDs. PK samples (patients > 20 kg in weight only) will be taken in accordance with Section 9.2.9.1.

The investigator must assess the patient's daily number of seizures from the patient's IVRS data, record the patient's attendance at the visit, and confirm the outcome of the visit prior to randomization. Patients who have experienced at least eight seizures during the first 28 days of the baseline period, and who meet all of the other inclusion and none of the exclusion criteria specified in Section 6, will be eligible to continue in the study.

Eligible patients will then be randomized to receive GWP42003-P 25 mg/kg/day, GWP42003-P 50 mg/kg/day, placebo 25 mg/kg/day dose volume equivalent, or placebo 50 mg/kg/day dose volume equivalent at a 2:2:1:1 ratio.

Following randomization at Visit 3, patients will remain at the clinic where the following baseline assessments will be performed prior to the administration of study medication: QOLCE/QOLIE-31-P, Wechsler Tests, CBCL/ABCL, SCQ and the Vineland-II. Suicidality will be assessed in accordance with Section 9.2.12.8.

Patients/caregivers and investigators will be asked to write a brief description of their/the patient's overall condition and assess the average duration of seizure subtypes as a memory aid for the PGIC, SGIC/CGIC and SGIC-SD/CGIC-SD; these will be referred to at relevant, subsequent visits or withdrawal.

IMP will be dispensed for the following 2 weeks and patients or their caregivers will be provided with individual dosing schedules as described in Section 8.1 Each patient will then receive a titration regimen. The first dose of IMP will be administered in clinic.

Following Visit 3, during titration, safety telephone calls must be made every two days. If the call falls on a weekend, it is permitted to schedule the call for the Friday before or Monday after the weekend instead. A further call must be completed one week after the end of titration. During these calls, caregivers will be asked for information on AEs, epilepsy-related hospitalizations, concomitant medications and/or changes to medication. The investigator must retain oversight of safety telephone calls.

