5.5.4.3 Rescue Medication Use

Blinded Phase:

The number of days that rescue medication (RM) was taken since the previous visit will be collected throughout the trial at scheduled visits and safety telephone calls.

To standardize between patients, the total number of days RM was taken will be calculated as the sum of all reported records within a period. Hence, the average number of days RM was taken per 28 days within a period will be calculated as follows:

$(\text{Total number of days RM was taken during the period} \div \text{Number of days in the period}) \times 28$

This will be calculated for both the baseline period and treatment period. The number of days in a period will be calculated as the number of days from the visit prior to the first recorded value in the period to the day of the last recorded value in the period. The baseline period refers to the period between Visit 2 and Visit 3. The treatment period refers to the period between Visit 3 and Visit 10.

The number of days RM was taken per 28 days will be summarized by period and treatment arm. The change from the baseline period will also be included.

The change from the baseline period to the treatment period will be analyzed using an ANCOVA approach. The model will include the baseline period and stratified age group as covariates and treatment arm as fixed factor.

The estimated least squares means, treatment difference, together with the 95% CIs and p-value will be presented.

Open-label Extension:

Descriptive summaries described above for the blinded phase will be repeated for the OLE period. The OLE period refers to the period between Visit B1 and the last available visit in the OLE phase.

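### Read literally, the SAP's rescue-medication rule adds overlapping records from visits and safety calls, counting treatment days about 1.8 times and baseline days once

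*Protocol*

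**What the plan says.** **Recording.** Under Protocol 9.2.11 the patient or caregiver "will also complete a paper diary daily to record AEs, concomitant AEDs, IMP intake and rescue medication throughout the study". In Protocol Appendix 1, the diary review that names rescue medication is scheduled at clinic visits.

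**Derivation.** In SAP 5.5.4.3 the number of days on which rescue medication "was taken since the previous visit will be collected throughout the trial at scheduled visits and safety telephone calls". Then "the total number of days RM was taken will be calculated as the sum of all reported records within a period". That sum is divided by the number of days in the period and multiplied by 28. The number of days is "the number of days from the visit prior to the first recorded value in the period to the day of the last recorded value". No rule deals with records that cover the same day.

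**Periods and analysis.** For baseline the SAP states: "The baseline period refers to the period between Visit 2 and Visit 3". For the comparison period after randomization it states: "The treatment period refers to the period between Visit 3 and Visit 10". The change between them goes into an ANCOVA with baseline and age group, giving a treatment difference, a 95% CI and a p-value. The same derivation is repeated descriptively for the OLE.

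**Contacts.** Protocol 9.1.1.3 says that "during titration, safety telephone calls must be made every two days", and 9.1.1.5 adds one call a week after titration ends. A call due on a weekend may move to the Friday or the Monday. Appendix 1 gives one schedule for all arms, with no safety call between Visit 2 and Visit 3.

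**Status.** Change in rescue medication use is an exploratory endpoint (Protocol 4.1.2; SAP 3.3.3 and 5.5.4). It is not in the testing hierarchy (SAP 5.5.1, Table 3).

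**The concern.** The denominator counts each calendar day once. The numerator counts a rescue day once for every record whose look-back reaches it. If a record taken at a call looks back to the last scheduled visit, every call in an interval repeats the earlier ones, and the next visit repeats them all again. Rescue use on Day 2 would be reported at the calls on Days 3, 5, 7, 9, 11 and 13 and once more at Visit 4.

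Baseline has only visit records, so it is free of this. The scored change from baseline would then mix any real change with a change in counting method. The weight given to each day would follow the call calendar and not the length of the period.

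**Working it through.** The documents give no figure to reproduce, so this is a direct count.

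**Inputs**
- Visits: Days 1, 15, 29, 43, 57, 71 (telephone), 85 and 113 (Protocol 4.1).
- Calls: every two days in titration, so Days 3 to 13 and 17 to 27, then Day 36 (Protocol 9.1.1.3 to 9.1.1.5).
- Literal reading: each record covers the days from the last scheduled visit up to the day before the contact. A day's weight is the number of records that cover it.

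**One 14-day titration interval.** Seven records (six calls and the visit) give daily weights 7, 7, 6, 6, … 1, 1. The sum is 2 × (7+6+5+4+3+2+1) = 56, and 56/14 = 4.0.

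**Treatment period**

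| Days | Number of days | Day-counts | Mean weight |
|---|---|---|---|
| 1–28 | 28 | 112 | 4.0 |
| 29–35 | 7 | 14 | 2.0 |
| 36–112 | 77 | 77 | 1.0 |
| Total | 112 | 203 | 203/112 = 1.81 |

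The baseline multiplier is 1.0.

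**Range.** Varying the weekday of Day 1 and the Friday/Monday rule gives 3.1 to 4.1 for Days 1–28 and 1.58 to 1.85 overall. If telephone Visit 8 is treated as a call and not as a visit, Days 57–70 are counted twice: (203 + 14)/112 = 1.94.

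**False rise.** Assume a constant 4 rescue days per 28. The treatment score is 4 × 1.8125 = 7.25, a rise of 3.25. At 2 per 28 the score is 3.63, a rise of 1.63. A true uniform fall of 1 − 1/1.8125 = 45% would be scored as no change.

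**Weight of early days.** Days 1–28 are 28/112 = 25% of the days and carry 112/203 = 55% of the weight. In the 25 mg/kg/day arm the target dose is reached on Day 9 (Protocol Table 8.1.2-1). Days before target there carry 2 × (7+6+5+4) = 44, and 44/203 = 22%.

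**Withdrawal.** The denominator stops at the last record, so a patient whose last record is at Day 29 has multiplier 112/28 = 4.0. At a constant 4 per 28 that patient scores 16, against 7.25 for a completer. If one arm has 10 percentage points more such patients (an assumption), the false difference in means is 0.10 × (16 − 7.25) = 0.875 days per 28. At 5 points it is 0.44.

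**Dilution.** Assume the drug halves rescue use on Days 29–112 only and placebo is constant. The true reduction against placebo is 42/112 = 37.5%. Maintenance carries 203 − 112 = 91 day-counts, so the scored reduction is 45.5/203 = 22%. The treated arm scores (112 + 45.5)/112 = 1.41 times baseline, a 41% rise where the truth is a 37.5% fall.

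**OLE.** Visits are on Days 1, 15, 36 and 92 and onward to 365. Calls run every two days to Day 35, with one on Day 43.
- Days 1–14: 56.
- Days 15–35: ten calls give 2+4+…+20 = 110, plus 21 at the visit, = 131.
- Days 36–91: 56 + 7 = 63.
- Days 92–364: 273.

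The total is 523, and 523/364 = 1.44.

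**Other reading.** If each record covers only the time since the previous contact, every day has weight 1, the multiplier is 1.00 throughout, and there is no false rise.

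**The case against.** **The meaning of *visit*.** The strongest objection is that the overlap depends on an undefined term. The documents sometimes call telephone contacts visits. Visit 8 is one, and SAP Table 2 lists Visit B12 with the label of a safety telephone call. SAP 5.6.4.5 uses the same look-back phrase for epilepsy hospitalizations, which the protocol also collects at safety calls. SAP 5.5.4.3 itself equates the sum of records with total days of use, which is true only if records do not overlap.

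On the other side, SAP 5.5.4.3 names visits and calls separately in one sentence. SAP Table 2 omits the titration calls, Protocol Appendix 1 gives them no visit number or day, and SAP 5.6.2 distinguishes a visit from a follow-up call. The literal wording therefore favours overlap, but the intention may have been otherwise. The CRF question would settle it and is not in the documents. A reader might infer that titration days certainly will be counted four times; the documents do not establish that.

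**Arm comparisons.** A reader might also infer a spurious treatment effect. Calls follow the same schedule in every arm, so a shared multiplier produces no difference when there is no effect. This objection stands, apart from the withdrawal and dilution routes worked above.

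**Titration as pre-target time.** It is tempting to say that days before target dose carry more than half the weight. That fits the 50 mg/kg/day schedule, which reaches target on Day 29. It does not fit the 25 mg/kg/day schedule, where the share is 22%.

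**The diary.** Daily diary entry does not contradict the SAP, because a diary can supply the counts reported at contacts. Nor do the documents show that paper-diary entries are databased. The SAP's diary listings cover IVRS data.

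**Conclusion.** The point holds as a conditional defect in the derivation. A programmer who follows SAP 5.5.4.3 literally obtains a wrong rate: about 1.8 times the true one over the treatment period (1.58 to 1.85 with weekend shifts), about 4.0 times in Days 1–28, and about 1.44 times in the OLE, against 1.0 at baseline. Every arm would appear to rise, early days would be over-weighted, and a maintenance effect would be diluted. A difference between arms could arise falsely if early withdrawal differs by arm, which is an assumption and not something the documents show.

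These figures assume that calls happen as scheduled, that calls do collect rescue days as the SAP states (the protocol's description of the calls does not name rescue medication), and that the look-back runs to the last scheduled visit. If the CRF asks about the time since the last contact, the data are sound and only the SAP text needs correction.

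The endpoint is exploratory, so no primary or key secondary result is affected. The text needs correcting on either reading.

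**What to change.** Amend SAP 5.5.4.3, for the blinded phase and the OLE, in one of two ways:

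1. Sum only the scheduled-visit records. Include telephone Visit 8 if it collects rescue use. If it does not, confirm that the Visit 9 record looks back to Visit 7, so that no days are lost.
2. Keep call records, but define each record as covering the time since the previous contact, whether visit or call, and verify this against the CRF question before programming.

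Either way, state that no calendar day may be counted twice. Distinct rescue dates from the daily paper diary, divided by diary days, would be an alternative only if those entries are databased.

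The cost is a short change to the SAP text and the derivation code, plus a look at the CRF. The first two options need no new data. The diary option could require data entry.

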### 9.2.12 Questionnaires and Assessments Completed at Scheduled Visits

Questionnaires should be completed by the patient or the caregiver, as appropriate. The same person should answer/complete the questionnaires/assessments in order to maintain consistency. The C-SSRS/Children's C-SSRS (where applicable) will be administered by a trained rater.

#### 9.2.12.1 Subject/Caregiver Global Impression of Change

The SGIC/CGIC, as appropriate, will be performed for all patients. At Visit 3 the patient or patient's caregiver will be asked to write a brief description of the patient's overall condition as a memory aid for the SGIC/CGIC at subsequent visits. It is preferred that the same person performs this assessment at each visit.

The CGIC comprises the following question to be rated on a seven-point scale:

• Since your child started treatment, please assess the status of your child's overall condition (comparing their condition now to their condition before treatment) using the scale below.

The SGIC comprises the following question to be rated on a seven-point scale:

• Since you started treatment, please assess the status of your overall condition (comparing your condition now to your condition before treatment) using the scale below.

The markers are: Very Much Improved; Much Improved; Slightly Improved; No Change; Slightly Worse; Much Worse; Very Much Worse.

If the main caregiver is not available at the appropriate visit then this information can be captured over the telephone, ideally on the day of the visit or otherwise within three days.

#### 9.2.12.2 Physician Global Impression of Change

The PGIC will be performed for all patients. At Visit 3 the investigator will be asked to write a brief description of the patient's overall condition as a memory aid for the PGIC at subsequent visits. It is preferred that the same investigator performs this assessment at each visit.

The PGIC comprises the following question to be rated on a seven-point scale:

• Please assess the change in the patient's general functional abilities since Visit 3 (prior to the commencement of study medication).

The markers are: Very Much Improved; Much Improved; Slightly Improved; No Change; Slightly Worse; Much Worse; Very Much Worse.

If the main caregiver is not available at the appropriate visit then this information can be captured over the telephone, ideally on the day of the visit or otherwise within three days.

#### 9.2.12.3 Subject/Caregiver Global Impression of Change in Seizure Duration

The caregiver will be asked to assess the average duration of the patient's seizures at Visit 3 (i.e., prior to commencement of IMP) as a memory aid for subsequent visits.

The SGIC-SD/CGIC-SD comprises a question to be rated on a three-point scale for each seizure subtype:

The markers are: Average duration of seizures has decreased; Average duration of seizures has stayed the same; Average duration of seizures has increased.

If the main caregiver is not available at the appropriate visit then this information can be captured over the telephone, ideally on the day of the visit or otherwise within three days.

#### CGIC-SD:

• Since the patient started treatment, please assess the average duration of the patient's seizures (comparing their condition now to their condition before treatment) using the scale below.

#### SGIC-SD:

• Since you started treatment, please assess the average duration of your seizures (comparing their condition now to their condition before treatment) using the scale below.

## 9.2.12.4 Quality of Life in Childhood Epilepsy (18 Years of Age and Younger) or Quality of Life in Epilepsy (19 Years of Age and Older)

The QOLCE and the QOLIE-31-P are composed of 16 and 31 subscales, respectively, assessing seven domains of Health Related Quality of Life (physical function, social function, emotional well-being, cognition, behavior, general health and general quality of life). The QOLCE (and QOLIE-31-P, if completed by the caregiver) must be completed by a person who interacts with the patient on a consistent, daily basis. Quality of life assessments will be performed for all patients. The questionnaires should take 20–30 minutes to complete.

#### 9.2.12.5 Vineland Adaptive Behavior Scales, Second Edition

The Vineland-II is an individually administered instrument for assessing adaptive behaviors. Communication, Daily Living Skills, Socialization, and Motor Skills will be assessed by the caregiver using a rating scale. Vineland-II assessments will be performed for all patients.

#### 9.2.12.6 Child/Adult Behavior Checklist

Achenbach CBCL and ABCL, for ages  $1\frac{1}{2}-5$ , 6-18 and 18-59 examine internalizing behaviors (such as depression and anxiety), externalizing behaviors (such as aggression), stress, obsessive-compulsive behaviors and 'sluggish cognitive tempo'. Statements about the patient's behavior are recorded on a Likert scale: 0 = Not True, 1 = Somewhat or Sometimes True, 2 = Very True or Often True.

The age appropriate checklist will be used for all patients.

#### 9.2.12.7 Social Communication Questionnaire

The current version of the SCQ will be completed by the caregiver for all patients above the age of 4 years with a mental age of at least 2 years. The scale provides

sub-scores to assess the domains Reciprocal Social Interaction, Communication and Restricted, Repetitive and Stereotyped Patterns of Behavior. The scale assesses behavior over the most recent three month period using 40 questions, each to be answered 'yes' or 'no'.

